4.2 General Registration Procedures

Confirm eligibility as defined in the section entitled [Patient Selection](#).

Obtain informed consent by following procedures defined in section entitled [Informed Consent Procedures](#).

During the registration process, registering individuals will be required to complete a protocol specific Eligibility Checklist. The individual signing the Eligibility Checklist is confirming that the participant is eligible to enroll in the study. Study staff are responsible for ensuring that all institutional requirements necessary to enroll a participant to the study have been completed. See related Clinical Research Policy and Procedure #401 (Protocol Participant Registration).

5. TREATMENT AND IMAGING PLAN

5.1 Agent Administration

Treatment will be administered on an outpatient basis. Reported adverse events and potential risks are described in [Section 7](#). Appropriate dose modifications are described in [Section 6](#). No investigational or commercial agents or therapies other than those described below may be administered with the intent to treat the patient's malignancy (except for thyroid hormone TSH suppression, palliative radiation to a non-target lesion, or therapy to prevent pathologic fractures caused by bone metastases (e.g. zoledronic acid and denosumab)).

5.1.1 Trametinib

Regimen Description					
Agent	Premedications; Precautions	Dose	Route	Schedule	Cycle Length
Trametinib	None	2 mg	Orally	Daily	28 days (4 weeks) (please see below for specifics regarding time on treatment)

- After completion of the first ^{124}I PET/CT lesional dosimetry process, all patients will start trametinib (Week 1, Day 6). Patients will remain on trametinib for about 4 weeks through the completion of the second ^{124}I PET/CT lesional dosimetry process.
- Ideally, patients will remain on trametinib continuously for a minimum of 7 days prior

to the PET/CT scan for the second lesional dosimetry (this is not a requirement). To achieve this, protocol assessments and treatments may be rescheduled (including but not limited to the second ^{124}I PET/CT lesional dosimetry, ^{131}I dosimetry/therapy, and/or repeating Thyrogen injection administration) at the discretion of the treating physician. Extending time on trametinib in this manner will not be considered a protocol violation. If the second ^{124}I PET/CT lesional dosimetry is delayed more than 4 weeks, the MSK Principal Investigator and the treating physician will determine if the patient should be continued or removed from the study. Please note that missing less than 7 dose(s) of study drug in a cycle for reasons other than toxicity issues will not be considered a violation of the protocol.

- Generally, missed doses do not need to be made up. However, making up missed doses may be considered if necessary to ensure that the patient has remained on trametinib for a minimum of 7 consecutive days as discussed above. If trametinib is missed for ≥ 7 days total or interruptions in trametinib dosing have occurred prior to or during whole body and blood dosimetry and ^{131}I (RAI) treatment, then having some or all of the doses made up and rescheduling the study assessments/treatments may be considered after discussion with the MSK Principal Investigator (this is not a requirement). Please note that missing less than 7 dose(s) of study drug in a cycle for reasons other than toxicity issues will not be considered a violation of the protocol.
- If lesional dosimetry with the second ^{124}I PET/CT scan reveals that a dose of $\geq 2,000$ cGy can be delivered to at least one tumor with ≤ 300 mCi of RAI, then the treating physician(s) will make a clinical decision as to whether ^{131}I therapy should proceed. If ^{131}I is to be given, the patient will continue trametinib until 2 days after therapeutic RAI has been administered. If therapeutic RAI will not be given, it will be concluded that the patient's cancer is still refractory to RAI and he/she will not receive RAI. Such patients may be continued on trametinib alone if 1) the treating physician determines it to be clinically reasonable, and 2) the patient agrees to continue on trametinib. If these conditions are not met, then trametinib will be discontinued and the patient will be removed from the study.
- The impact of more than one month of trametinib therapy upon RAI uptake and/or efficacy is unknown. Patients who do not receive ^{131}I therapy after the second ^{124}I PET/CT scan and remain on trametinib may be evaluated with a third Thyrogen-stimulated ^{124}I PET/CT scan (with the procedure detailed in Section 10.0 for Week 5) 4 weeks or more after completion of the prior ^{124}I PET/CT scan process. If the lesional dosimetry criteria for ^{131}I therapy is met on the third ^{124}I PET/CT, patients can go on to be prepared for/treated with ^{131}I and followed as detailed in Section 10.0 (in the calendar under the heading "*Study Calendar for PATIENTS WHO RECEIVE RAI (Week 5, Day 6 and beyond)*" (treatment with ^{131}I is not mandatory). If the third ^{124}I PET/CT scan results do not fulfill the ^{131}I treatment criteria, patients may continue on trametinib alone with the evaluations/treatments required for Cohort C.
- The effect of food on trametinib absorption is unknown. The current recommendation is to administer trametinib on an empty stomach, either 1 hr before or 2 hr after a meal; the recommendation to administer trametinib fasting may change based on emerging data.
- The patient will be requested to maintain a medication diary for each dose of medication ([Appendix C](#)). The medication diary will be returned to clinic staff at the

end of each course.

5.1.2 Diagnostic Agent thyrotropin alpha (Thyrogen;Genzyme)

Patients will undergo ^{124}I PET/CT scanning after thyrotropin alpha (Thyrogen;Genzyme Corp., Cambridge, MA) 0.9 mg IM daily injections (for two consecutive days) as previously described (Robbins et al., 2002). Thyrogen contains a highly purified recombinant form of human thyroid stimulating hormone (TSH), and is FDA approved for thyroid dosimetry.

5.1.3 Diagnostic/Therapeutic Agent ^{131}I (RAI)

^{131}I will be used for dosimetry studies and treatment of the patients whose second lesional dosimetry reveals iodine incorporation that satisfies the ^{131}I treatment threshold (see [Section 5.1.4](#)). ^{131}I has a half-life of 8 days and relatively high principal photon energy of 364 keV characterized by beta particle emissions. It will be supplied by MDS Nordion , DraxImage, or International Isotopes. It is administered orally in the form of capsules or liquid. Pregnancy is the only contraindication to radioiodine treatment. A beta-HCG pregnancy test must be performed up to 2 days prior to the administration of ^{131}I .

^{131}I therapeutic dosing will be guided by the whole body and blood dosimetry determination of the maximum tolerated activity (MTA): the ^{131}I activity administered concomitantly with trametinib is not to exceed the MTA plus 3 mCi (i.e., [^{131}I activity administered] \leq [MTA + 3 mCi]).

5.1.4 Diagnostic Agent ^{124}I PET tracer

Clinical grade ^{124}I was first produced at MSK in the 1950s. It has been produced in MSK cyclotrons by bombarding tellurium targets. It is purified by novel radiochemical techniques. It has been safely used for diagnostic studies in >40 thyroid cancer patients at MSK for over 5 years. Clinical grade ^{124}I will be provided by the MSK cyclotron staff or by an outside supplier (Sofie Biosciences (fka IBA Molecular and Zevacor), 3 D Imaging LLC, or NCM) who meets MSK's minimum specifications as stated in our IND. ^{124}I preparation is detailed in MSK held IND # 71343. Normal organ dosimetry of ^{124}I is provided in [Appendix D](#) (Note, this is a general guideline for organ dosimetry).

^{124}I (dose, route, timing relative to imaging, special precautions or procedures, required pre-administration lab parameters): Approximately 6 mCi (range 4-7 mCi) of ^{124}I will be administered orally on Day 3 of the lesional dosimetry protocol, 2 days prior to PET/CT image acquisition (see [Section 10](#) for the Study Calendar). A beta-HCG pregnancy test must be performed within 2 days prior to the administration of ^{124}I .

Image Acquisition/Analysis/Interpretation Details: Since ^{124}I PET/CT analysis will be performed at more than one participating site, before patients are imaged at any site a NEMA/IEC body phantom will be imaged and results analyzed under conditions similar to those to be used for patients. The phantom approximates the size and shape of a typical adult cross-section and contains six fillable spheres of diameter ranging from 10mm to 37mm surrounding a central cylindrical compartment containing non-radioactive lung equivalent material. The spheres and outer background compartment will be filled with ^{124}I of precisely known activity concentration in the ratio of 5:1. The

activity concentration will be determined from the supplier's activity measurement (recommended activity approximately 150MBq (4mCi)) and a confirming measurement in a dose calibrator at the site using an approved calibration setting, followed by careful dilution and measurement of residual activities. Following a scan of sufficient length to cover the whole phantom (two bed positions with ten minutes per bed for the phantom, patients will need more), data should be reconstructed with appropriate clinical parameters for the scanner used. These should include CT attenuation correction, scatter correction, and parameters specific to I^{124} – 4.18 day half life, 0.23 positron abundance, and a cascade gamma correction. SUV's and activity concentrations within each sphere, the active background, the central lung compartment, and outside the phantom should be determined using an appropriate VOI as for a patient. After applying partial volume recovery coefficients appropriate for the scanner used and for the individual sphere size, all measurements should match the activity concentrations derived from the dose calibrator measurements. Any discrepancies should be addressed. The resolution will depend on the cause and may involve modification of technique or possibly a correction factor. Raw data, a record of all measurements, procedures and parameters used, and results for the phantom study should be forwarded to MSK for review before commencing patient imaging.

The I^{124} PET-CT scan will be performed on a PET/CT scanner at 2 days post-administration of approximately 6 mCi (range 4-7 mCi) of I^{124} , the time at which maximal uptake of iodide by thyroid tumors generally occurs. The index lesion (i.e. metastatic thyroid tumor) will be identified by radiology co-investigators. The index lesion volume (in milliliters, ml), V_{lesion} , will be estimated by the CT study performed for attenuation correction and anatomic registration as part of the I^{124} PET-CT scan on the PET/CT scanner. Once reconstructed, and using the commercial image-processing software provided on the PET/CT scanner's computer or a compatible, networked workstation, regions of interest (ROIs) circumscribing the index lesion on all contiguous CT slices on which the lesion appears will be drawn, yielding V_{lesion} . **Only lesions on the first I^{124} PET-CT scan that are ≥ 5 mm in length in the minimum diameter will be used as the index lesion for this analysis.**

Using the PET acquisition and processing parameters routinely used for PET-CT scans at the participating sites, the reconstructed PET images will be parameterized, as usual, in terms of standard uptake value (SUV) ($\equiv \mu\text{Ci measured by PET/g of tissue} / \mu\text{Ci administered/g of total-body mass}$). Using the commercial image-processing software provided on the PET/CT scanner's computer or a compatible workstation, ROIs circumscribing the index lesion on all contiguous PET slices on which the lesion appears

will be drawn, yielding the index lesion mean SUV, \overline{SUV}_{lesion} ; alternatively, the lesion ROIs drawn on the CT scan (see above) may be superimposed on the registered PET

images to yield \overline{SUV}_{lesion} . From the definition of the SUV (above), the mean PET-derived I^{124} concentration (in $\mu\text{Ci/ml}$) in the index lesion not corrected for partial-

volume-averaging, ($\overline{[{}^{124}\text{I A}]}_{\text{lesion}}$)_{RC-uncorrected}, will be calculated from $\overline{\text{SUV}}_{\text{lesion}}$:

$$(\overline{[{}^{124}\text{I A}]}_{\text{lesion}})_{\text{RC-uncorrected}} = \overline{\text{SUV}}_{\text{lesion}} \frac{\text{AA}}{\text{MTB}} \quad (1)$$

where AA is the ${}^{124}\text{I}$ administered activity (in μCi) and MTB is the patient total-body mass (in μCi).

Note that the SUVs provided by the PET scanner are *not* automatically corrected for partial-volume averaging. Using the CT-derived lesion volume, V_{lesion} , and the volume (V)-dependent recovery coefficient (ie PET-derived activity concentration (in $\mu\text{Ci}/\text{ml}$)/actual activity concentration (in $\mu\text{Ci}/\text{ml}$)), $\text{RC}(V)$, previously measured for the PET/CT scanner, the PET-derived mean ${}^{124}\text{I}$ concentration (in $\mu\text{Ci}/\text{ml}$) in the index

lesion *not* corrected for partial-volume-averaging, ($\overline{[{}^{124}\text{I A}]}_{\text{lesion}}$)_{RC-uncorrected}, will be corrected to yield the actual mean ${}^{124}\text{I}$ concentration in the index lesion, ($\overline{[{}^{124}\text{I A}]}_{\text{lesion}}$)_{RC-corrected}:

$$(\overline{[{}^{124}\text{I A}]}_{\text{lesion}})_{\text{RC-corrected}} = \frac{(\overline{[{}^{124}\text{I A}]}_{\text{lesion}})_{\text{RC-uncorrected}}}{\text{RC}(V_{\text{lesion}})} \quad (2)$$

The mean ${}^{124}\text{I}$ activity concentration in the index lesion per ${}^{124}\text{I}$ administered activity (in $\mu\text{Ci}/\text{ml}/\text{mCi}$), ($\overline{[{}^{124}\text{I A}_{\text{per mCi}}]}_{\text{lesion}}$)_{RC-corrected}, will then be calculated:

$$(\overline{[{}^{124}\text{I A}_{\text{per mCi}}]}_{\text{lesion}})_{\text{RC-corrected}} = \frac{(\overline{[{}^{124}\text{I A}]}_{\text{lesion}})_{\text{RC-corrected}}}{\text{AA}/1000} \quad (3)$$

($\overline{[{}^{124}\text{I A}_{\text{per mCi}}]}_{\text{lesion}}$)_{RC-corrected} can be converted to the mean ${}^{131}\text{I}$ activity concentration in the index lesion per ${}^{131}\text{I}$ administered activity (in $\mu\text{Ci}/\text{ml}/\text{mCi}$), ($\overline{[{}^{131}\text{I A}_{\text{per mCi}}]}_{\text{lesion}}$)_{RC-corrected}, ${}^{131}\text{I}$ (and not ${}^{124}\text{I}$) being used for therapy:

$$(\overline{[{}^{131}\text{I A}_{\text{per mCi}}]}_{\text{lesion}})_{\text{RC-corrected}} = (\overline{[{}^{124}\text{I A}_{\text{per mCi}}]}_{\text{lesion}})_{\text{RC-corrected}} e^{(\lambda_{\text{I}124} - \lambda_{\text{I}131})t_{\text{imaging}}} \quad (4)$$

where $\lambda_{\text{I}124}$ and $\lambda_{\text{I}131}$ are the physical decay constants of ${}^{124}\text{I}$ (0.00693 /h) and ${}^{131}\text{I}$ (0.00359 /h), respectively, and t_{imaging} is the time post-administration of PET-CT imaging (in h).

Based on prior clinical experience, the biological half-life, T_b , of iodine in metastatic thyroid cancer lesions is typically 2 d (= 48 h). For ${}^{131}\text{I}$, with a physical half-life T_p of

8.04 d = 193 h, the effective half-life, T_e , of ^{131}I in the index lesion is therefore:

$$T_e = \frac{T_b T_p}{T_b + T_p} \quad (5a)$$

$$= \frac{48 \text{ h} \cdot 193 \text{ h}}{48 \text{ h} + 193 \text{ h}} \quad (5b)$$

$$= 38.4 \text{ h} \quad (5c)$$

Assuming, as usual, that the uptake of radioiodine in the index lesion (ie the 24- to 48-h uptake value) will be instantaneous and that ^{131}I lesion irradiation will be due exclusively to complete local absorption of ^{131}I beta-rays, the mean lesion absorbed dose (in rad/mCi ^{131}I), $[\overline{^{131}\text{I} D_{\text{per mCi}}}]_{\text{lesion}}$, will be:

$$[\overline{^{131}\text{I} D_{\text{per mCi}}}]_{\text{lesion}} = 1.44 T_e ([\overline{^{131}\text{I} A_{\text{per mCi}}}]_{\text{lesion}})_{\text{RC-corrected}} \Delta_{\text{np}} \quad (6a)$$

$$= 1.44 \cdot 38.4 \text{ h} ([\overline{^{131}\text{I} A_{\text{per mCi}}}]_{\text{lesion}})_{\text{RC-corrected}} \\ 0.405 \text{ g-rad}/\mu\text{Ci-h} \quad (6b)$$

$$= 22.4 ([\overline{^{131}\text{I} A_{\text{per mCi}}}]_{\text{lesion}})_{\text{RC-corrected}} \quad (6c)$$

where $\Delta_{\text{np}} = 0.405 \text{ g-rad}/\mu\text{Ci-h}$ is the equilibrium dose constant for non-penetrating radiations (ie beta-rays) for ^{131}I .

Finally, the ^{131}I administered activity (in mCi) required to deliver the stipulated mean absorbed dose of 2,000 rad to the index lesion, $^{131}\text{I} AA_{2000 \text{ rad} \rightarrow \text{lesion}}$, will be:

$$^{131}\text{I} AA_{2000 \text{ rad} \rightarrow \text{lesion}} = 2,000 \text{ rad}/[\overline{^{131}\text{I} D_{\text{per mCi}}}]_{\text{lesion}} \quad (7)$$

If the projected $^{131}\text{I} AA_{2000 \text{ rad} \rightarrow \text{lesion}}$ is reasonable ($\leq 300 \text{ mCi}$), the treating physician(s) will confer and make a clinical decision as to whether ^{131}I therapy should proceed. If the decision is made to proceed to therapy, the patient will undergo the standard-of-care (ie non-investigational) “whole body and blood dosimetry” to determine the maximum tolerated activity (MTA). ^{131}I therapeutic dosing will be guided by the whole body and blood dosimetry determination of the maximum tolerated activity (MTA): the ^{131}I activity administered concomitantly with trametinib is not to exceed the MTA plus 3 mCi (i.e., $[^{131}\text{I} \text{ activity administered}] \leq [\text{MTA} + 3 \text{ mCi}]$).

The foregoing analysis will have to be performed only for the second ^{124}I administration.

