1. OBJECTIVES

1.1 Primary Objectives

For Cohort A (RAS mutant (MUT) thyroid cancer patients):

- 1) To evaluate the effect of trametinib on enhancing radioiodine (RAI) activity by determining the proportion of patients alive at 6 months without disease progression by RECIST v1.1 criteria following treatment with RAI in co-administration with trametinib.
- 2) To evaluate the effect of trametinib on enhancing RAI activity by determining the objective response rate (ORR) at 6 months following treatment with radioiodine (RAI) in co-administration with trametinib.

For Cohort B (BRAF/RAS wild-type (WT) thyroid cancer):

To determine the proportion of patients following trametinib therapy with increased tumoral iodine incorporation as quantified by ^{124}I PET/CT lesional dosimetry.

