Rationale for evaluating trametinib in RAI-refractory thyroid cancer

The selumetinib pilot study demonstrated that MEK inhibition can enhance iodine incorporation to induce clinical responses in a subset of patients with RAI-refractory thyroid cancer. A particularly promising signal was observed in *RAS* MUT patients as all 5 enrolled in the pilot had a positive ^{124}I response with selumetinib. However, the limited number of *RAS* MUT patients treated on the study requires that further investigation be performed to better assess clinical efficacy. Cohort A of this study will be dedicated to evaluating the clinically efficacy of MEK inhibition with trametinib in combination with RAI only in patients with *RAS* MUT, RAI-refractory thyroid cancer. Cohort B will explore if MEK inhibition with trametinib can be effective for enhancing iodine incorporation in *BRAF/RAS* WT tumors, a genotype subset that

was less susceptible to selumetinib in the pilot study. In both cohorts, $^{124}\text{PET}/\text{CT}$ lesional dosimetry will be used to quantify changes in tumoral iodine incorporation induced by trametinib.

Trametinib was the agent selected for investigation based on emerging evidence that the clinical efficacy of MAPK pathway targeted therapies likely is related to the potency of signaling inhibition. In the phase I study of the BRAF kinase inhibitor PLX4032 for *BRAF* MUT cutaneous melanoma, only patients with tumors demonstrating near complete inhibition of ERK phosphorylation (80% or greater) experienced tumor regressions; partial pathway inhibition resulted in little or no change in tumor dimensions (Bollag *et al.*, 2010). In a randomized phase II study of 99 melanoma patients treated with selumetinib, only 6 (5.8%) partial responses were observed, indicating that the vast majority of the estimated 46.2% of patients with *BRAF* MUT disease on the trial did not respond to selumetinib (Kirkwood *et al.*, 2011). In comparison, the phase III trial comparing trametinib to chemotherapy for patients with *BRAF* *MUT* cutaneous melanoma reported an overall response rate of 22% in the trametinib group (Flaherty *et al.*, 2012). It is possible that the efficacy observed with trametinib reflects enhanced potency for inhibiting the MAPK pathway. Therefore, we hypothesize that trametinib may be as effective as selumetinib for enhancing iodine incorporation in *RAS* MUT patients, and perhaps more effective for *BRAF/RAS* WT patients.

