3. PATIENT SELECTION

3.1 Inclusion Criteria

For both Cohort A and B patients:

3.1.1 Patients must have histologically or cytologically confirmed thyroid carcinoma of follicular origin (including papillary, follicular, or poorly differentiated subtypes and their respective variants). Confirmation of thyroid carcinoma will be done at MSK.

3.1.2 Patients must have measurable disease, defined as at least one lesion that can be accurately measured in at least one dimension (longest diameter to be recorded for non-nodal lesions and short axis for nodal lesions) as ≥ 20 mm with conventional techniques or as ≥ 10 mm with spiral CT scan, MRI, or calipers by clinical exam. See [Section 11](#) for the evaluation of measurable disease. Tumors in previously irradiated fields may be considered measurable if there is evidence of tumor progression after radiation treatment.

3.1.3 RAI-refractory disease on structural imaging, defined as any one of the following:

- a) A metastatic lesion that is not radioiodine-avid on a diagnostic radioiodine scan performed prior to enrollment in the current study, or
- b) A radioiodine-avid metastatic lesion which remained stable in size or progressed despite radioiodine treatment 6 months or more prior to entry in the study. There are no size limitations for the index lesion used to satisfy this entry criterion.
- c) The presence of at least one fluorodeoxyglucose (FDG) avid lesion.

3.1.4 No recent treatment for thyroid cancer as defined as:

- a) No prior RAI therapy is allowed < 6 months prior to initiation of therapy on this protocol. A diagnostic study using < 10 mCi of RAI is not considered RAI therapy.
- b) No external beam radiation therapy < 4 weeks prior to initiation of therapy on this protocol. (Previous treatment with radiation for any indication is allowed if

the investigator judges that the previous radiation does not significantly compromise patient safety on this protocol.)

- c) No chemotherapy or targeted therapy (e.g., tyrosine kinase inhibitor) is allowed < 4 weeks prior to the initiation of therapy on this protocol.

3.1.5 Age \geq 18 years. Because no dosing or adverse event data are currently available on the use of trametinib alone or in combination with RAI in patients < 18 years of age, children are excluded from this study.

3.1.6 ECOG performance status \leq 2 (Karnofsky \geq 60%, see [Appendix A](#)).

3.1.7 Life expectancy of greater than 3 months.

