The analysis of progression or death will capture the potential benefit of disease control without continuous treatment that the study strategy provides (as opposed to indefinite, continuous chemotherapy). The pilot study evaluating selumetinib enhancement of RAI therapy had similar eligibility requirements to those in this study, except that the pilot did not require radiographic evidence of disease progression prior to enrollment as this study does. Still, an unplanned, retrospective analysis of 16 patients on the pilot selumetinib study revealed that 15 had evidence of tumor progression on imaging up to one year prior to enrollment, suggesting that the disease for this patient population generally has a propensity to progress. In a phase II study evaluating gefitinib for RAI-refractory thyroid cancer patients (disease progression prior to enrollment was not required) in which some minor reductions in tumor size but no RECIST responses were observed, the median progression-free survival was only 3.9 months (Pennell et al., 2008), corresponding to a 6-month PFS of 34% (under exponential distribution assumption). Because our study requires progression of disease at enrollment, we expect a higher progression rate, therefore assumed a 20% 6-month PFS (null hypothesis). Since all the RAI-refractory patients on the pilot selumetinib study with enhanced RAI incorporation had durable partial responses or stable disease up to 6 months following RAI, we are targeting 50% of patients to be progression-free at the 6 month time point with treatment on this study. For ORR, the assumption that only 5% of these patients would have a RECIST response with RAI alone at the 6-month time point is based upon the premise that we are enrolling a population deemed refractory to RAI alone according to clinical criteria.

Cohort B (BRAF/RAS WT): The primary objective for this arm will be to explore if treatment with trametinib can increase iodine incorporation in thyroid cancer metastases to a predicted lesional absorbed radiation dose equal to or exceeding 2,000 cGy with the administration of \leq

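### The iodine-uptake endpoint is described as an increase caused by trametinib but scored only as a level on the second scan, so uptake present before the drug can count as a response

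*Combined protocol and SAP*

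**What the plan says.** Several sections describe a change from before to after trametinib.

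- **Section 1.1, Cohort B primary objective:** "To determine the proportion of patients following trametinib therapy with increased tumoral iodine incorporation". Section 1.2 gives Cohort A the same aim as a secondary objective.
- **Section 2.4, rationale for trametinib:** in both cohorts, "lesional dosimetry will be used to quantify changes in tumoral iodine incorporation induced by trametinib".
- **Section 13.1, Cohort B:** the aim is to explore whether "treatment with trametinib can increase iodine incorporation in thyroid cancer metastases to a predicted lesional absorbed radiation dose" of 2,000 cGy or more with at most 300 mCi. Section 13.4 defines an adequate increase in Cohort A by the same threshold.

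The operational text concerns the second scan.

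- **Section 5.1.1** applies the threshold to the second scan and needs only one tumour to meet it.
- **Section 5.1.4**, after equations 1 to 7: "The foregoing analysis will have to be performed only for the second" ¹²⁴I administration. Its stated use of the first scan is to qualify lesions by size: only those of at least 5 mm "in length in the minimum diameter will be used as the index lesion for this analysis".

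A scan before the drug does exist. After the first ¹²⁴I PET/CT "lesional dosimetry process, all patients will start trametinib (Week 1, Day 6"), with no separate path for patients already at threshold. Section 13.1 declares Cohort B positive if at least 3 of 10 patients meet the criterion, and puts the chance of this at 7% or less when the true rate is below 10%.

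**The concern.** In a single-arm cohort, the claim that the drug raised uptake rests on the comparison with the same patient before the drug. The plan acquires the scan for that comparison but requires no dose from it, no same-lesion pairing and no minimum change. It is also silent on a patient who already meets the criterion on the first scan, so nothing stops that patient being counted as a response.

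Eligibility does not close the gap. Criterion 3.1.3b admits "A radioiodine-avid metastatic lesion which remained stable in size or progressed despite radioiodine treatment 6 months or more prior to entry in the study", and 3.1.3c asks only for "The presence of at least one fluorodeoxyglucose (FDG) avid lesion", with no condition on iodine uptake.

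For Cohort B the inference from its only decision rule is at stake. In Cohort A the endpoint is a proportion with an exact confidence interval, so no decision error attaches, but the estimate could mix baseline uptake with drug effect.

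**Working it through.** **Inputs from Section 13.1 (Cohort B).** n = 10; positive if X ≥ 3; null rate 10%; stated error 7% or less.

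**Assumed inputs.** The documents do not give b, the share of patients at threshold on the first scan, or q, the share of the remainder whom trametinib newly brings to threshold. Ranges are shown for b. For q the values are 0, 10% (the plan's null read as a conversion rate) and 40% (an illustrative active drug).

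**1. The plan's own figure.**

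P(X ≥ 3) = 1 − 0.9¹⁰ − 10(0.1)(0.9⁹) − 45(0.1²)(0.9⁸) = 1 − 0.3487 − 0.3874 − 0.1937 = 0.0702.

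The stated 7% is reproduced. It is the error for the rate of being at threshold on the second scan, which differs from the rate of drug-induced increase whenever b > 0.

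**2. Inert drug, scoring on the second scan only.** Here q = 0, so p = b.

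| b | P(X ≥ 3 of 10) |
|---|---|
| 5% | 0.0115 |
| 10% | 0.0702 |
| 15% | 0.1798 |
| 20% | 0.3222 |

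The stated error is exceeded only when b is above 10%.

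**3. Null read as 10% conversion among patients below threshold.** With scoring on the second scan only, p = b + 0.1(1 − b). With paired scoring and patients already at threshold kept as non-responses, p = 0.1(1 − b).

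| b | p, second scan only | P(X ≥ 3) | p, paired | P(X ≥ 3) |
|---|---|---|---|---|
| 5% | 0.145 | 0.1670 | 0.095 | 0.0618 |
| 10% | 0.190 | 0.2922 | 0.090 | 0.0540 |

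**4. Single patients matter at n = 10.** Suppose exactly one patient is at threshold at baseline and the other nine convert at 10%. Two more responses are then enough: 1 − 0.9⁹ − 9(0.1)(0.9⁸) = 0.225. Three such patients who stay at threshold meet the rule with no drug effect at all.

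**5. Power under paired scoring.** With 40% conversion, p = 0.4(1 − b).

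| b | p | P(X ≥ 3) |
|---|---|---|
| 0 | 0.40 | 0.8327 |
| 5% | 0.38 | 0.7983 |
| 10% | 0.36 | 0.7595 |

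**The case against.** **The wording already implies a crossing.** A lesion above threshold at baseline has not been increased to it, and the Section 5.1.4 sentence sets a minimum: it does not forbid a baseline calculation. Both points are fair. The concept is present and the data exist. What is missing is the rule that makes the analyst compute the baseline dose and score on it.

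**b may be small, and the 10% null leaves room for it.** This stands as a limit on size. A 3.1.3b lesion was stable or grew despite radioiodine, while Section 2.3 places clinical responses at about 2,000 cGy. The selumetinib pilot in Section 2.4 used similar refractory criteria and gives no sign that patients reached threshold on baseline uptake alone. It reports no baseline doses, however, so it does not show that b is zero. As written, the plan does not ensure that b will be known.

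**The 16.7% and 29.2% figures rest on another reading of the null.** Correct. Section 13.1 does not state that reading, and the drug is not inert in that scenario, so these are not false-positive rates for an ineffective drug. The inert-drug figures are the ones to compare with 7%.

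**Paired scoring has its own edges.** A lesion rising from 2,000 to 6,000 cGy would not count, while one moving from 1,990 to 2,010 would, with no allowance for scan-to-scan variation. That is true of any threshold-crossing definition. This one follows the wording of Sections 13.1 and 13.4, and it removes the specific problem of crediting the drug with uptake already at threshold.

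**Cohort B is small and exploratory.** It nevertheless has a stated decision rule, a stated error and a stated conclusion about drug effect.

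**Conclusion.** The concern holds. The endpoint is described as an increase and scored as a level, the dose calculation is required only for the second scan, and patients already at threshold are not addressed. The binomial arithmetic in Section 13.1 is correct but does not control the error for the claim drawn from it.

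The size rests on the unknown b. If b is zero, the 7% stands. With an inert drug, the chance of a positive Cohort B result passes 7% only when b exceeds 10%, reaching 18.0% at 15% and 32.2% at 20%. The Cohort A co-primary endpoints are not affected. The finding is limited to the text, because the schema figure was not available. It should be fixed, since the remedy uses a scan already acquired.

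**What to change.** 1. In Section 5.1.4, replace the sentence limiting the calculation to the second administration with: *Equations 1–7 will be applied to the same index lesion(s) on both the first and the second ¹²⁴I PET/CT.*
2. In Section 13.1 (Cohort B response) and Section 13.4 (Cohort A adequate increase), use one definition: at least one index lesion that is below the threshold (2,000 cGy or more with 300 mCi or less) on the first scan and meets it on the second.
3. State that a patient whose only qualifying lesion already met the threshold at baseline is not a response. In Cohort B, that patient stays in the denominator of 10 for the decision rule, which is the conservative choice. List such patients separately.
4. Align the objectives in Sections 1.1 and 1.2 with this definition.

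This changes endpoint scoring only, not who receives ¹³¹I. The optional third scan needs no new rule here, because Section 13.4 already treats its results as exploratory and keeps outcomes after any resulting ¹³¹I separate from the Cohort A and B analyses.

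The cost is one extra dosimetry calculation per patient, with no new procedure, and some power if patients already at threshold are enrolled. Assuming 40% conversion, the chance of a positive result falls from 83.3% at b = 0 to 79.8% at b = 5% and 75.9% at b = 10%.
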